#### Siderosis group visits and investigations:

Siderosis group participants will be seen by the clinical team as part of their clinical care pathway and will undergo the following tests during their **first/initial visit in the Neuro-otology clinic:**

1. *Informed consent*
2. *Full neuro-otological examination:* full medical history; clinical examination of the head and neck, ears (otoscopy) and cranial nerves III/IV/VI/VII, (20mins)
3. *Pure tone audiometry (PTA)* for each ear measuring air and bone-conduction (15mins)
4. *Screening tympanogram* to check the function of the middle ear (5mins)
5. *Auditory Brainstem response (ABR) testing* on a calibrated ABR system; recorded with monaural alternating click stimuli; minimum intensity of 90dB (40mins)
6. *Vestibular nystagmography (VNG)/rotational chair testing:* including eye tracking/gaze nystagmus/positional nystagmus/optokinetic nystagmus/smooth pursuit/saccade tests (30mins)

7. *Video Head Impulse Test (vHIT)*: using appropriate software, goggles and in-built video-camera to record eye movements during unpredictably-timed and -directed head-rotations at speed 150-300degree/s (10mins)

At the first clinic visit the siderosis group the participants who have expressed interest in participating in the study will be seen by the research student. After confirming their eligibility and willingness to participate in the study, the potential participants will be formally consented and enrolled in the study. The research student and the study participant will arrange a suitable date/time for the research visit to take place.

During the research visit, the siderosis group participants will undergo the following:

1. Verification of the participant's eligibility to participate in the study and that the informed consent has been obtained (5mins)
2. Brief medical history and clinical examination (of ears/eyes/co-ordination) (5mins)
3. *Speech-in-quiet test* (10mins)
4. *Otoacoustic emissions (OAEs)* by delivering sound stimuli through a probe in the ear canal, using dual channel analyser (10mins)
5. *Stapedial (acoustic) reflex thresholds*: ipsilateral (same side) and contralateral (opposite side) measurements using a calibrated middle ear recorder at 0.5/1/2/4 kHz; range 70-120dB HL (5mins);

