**Comparison:**

The findings obtained following the audiological and the quality-of-life questionnaires will be compared between the siderosis group, the ARHL group, and the control group. The results of vestibular assessments will be compared to the age-matched normative data.

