## 5.5 Data analysis methods

Quantitative Analysis will be conducted using dedicated statistical software package.

Statistical analysis will be performed under the guidance and with advice of a designated biostatistician at UCL and/or at Biostatistics Office, UCL(H) Joint Research Office (JRO).

Each variable will be checked for distribution skewness, and regression models for each variable will be constructed. For binary variables, chi-square tests will be performed in order to determine the difference in the findings between the siderosis group and the control groups.

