#### 7.1.1 Siderosis group

Inclusion criteria:

- Adults (male and female) of 18+ years old with a known diagnosis of iSS confirmed by a consultant neurologist with expertise in this condition at University College London Hospitals (NHS Foundation Trust)

Exclusion criteria:

- Individuals with a physical or mental impairment that prevents the potential participant from giving informed consent or undergoing the audiological and/or vestibular assessment
- Individuals younger than 18 years old
- Individuals with no prior diagnosis of iSS

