#### 7.1.2 Age-related hearing loss (ARHL) group

Inclusion criteria:

- Adults (male and female) of 18+ years old with a known diagnosis of ARHL

Exclusion criteria:

- Individuals with a physical or mental impairment that prevents the potential participant from giving informed consent or undergoing the audiological assessment
- Individuals younger than 18 years old
- Individuals with diagnosis of hearing loss of aetiology other than age-related

- Individuals with history of exposure to high-intensity noise or ototoxic drugs or evidence of middle ear disease/dysfunction or family history of non age-related hearing loss
- Individuals with no previous diagnosis of age-related hearing loss

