### 7.1.3 Control group

Inclusion criteria:

- Adults (male and female) of 18+ years old with no previous diagnosis of hearing loss or no known neurological disorder (including iSS) that affects hearing (control group); we will aim to recruit such participants of 50 years of age and above, however if difficulty with recruitment of such participants arises, we will recruit participants of 18 years of age and above.

Exclusion criteria:

- Individuals with a physical or mental impairment that prevents the potential participant from giving informed consent or undergoing the audiological and assessment
- Individuals younger than 18 years old
- Individuals with a known history of hearing loss (of any cause) or with a known neurological disorder that affects their hearing
- Individuals with history of exposure to high-intensity noise or ototoxic drugs or evidence of middle ear disease or family history of non age-related hearing loss

Participants in the siderosis group will be users of the National Health Service (NHS) and will be recruited from University College London Hospitals (NHS Foundation Trust) London. The ARHL group participants will be recruited from the Adult Audiology Services at University College London Hospitals (NHS Foundation Trust), and will have used the NHS services in the past or will be recruited from the general public. The control group participants will be recruited from the general population. There will be no upper limit to the participants' age.

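### Four causes or markers of hearing loss are excluded from both comparator groups but not from the siderosis group, and section 5.5 states no analysis that accounts for the difference

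*Combined protocol and SAP*

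**What the plan says.** All eligibility and analysis text is in the combined protocol and SAP.

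- **ARHL group (7.1.2).** Excluded: individuals with a "history of exposure to high-intensity noise or ototoxic drugs or evidence of middle ear disease/dysfunction or family history of non age-related hearing loss".
- **Control group (7.1.3).** Excluded: individuals with a "history of exposure to high-intensity noise or ototoxic drugs or evidence of middle ear disease or family history of non age-related hearing loss". The only difference is that dysfunction of the middle ear is not mentioned.
- **Siderosis group (7.1.1).** Three exclusions: an impairment that prevents consent or testing, age under 18, and "Individuals with no prior diagnosis of iSS". None of the four factors appears.
- **Comparison (5.2).** The audiological and quality-of-life findings "will be compared between the siderosis group, the ARHL group, and the control group".
- **Analysis (5.5).** After a check for skewness, "regression models for each variable will be constructed". Yes/no outcomes are handled by a different method: "chi-square tests will be performed in order to determine the difference in the findings between the siderosis group", with the comparators on the other side. No covariate, restriction, stratification or sensitivity analysis is named.
- **Data already collected in the siderosis group (5.2).** The clinic visit includes "full medical history; clinical examination of the head and neck, ears (otoscopy) and cranial nerves", air- and bone-conduction audiometry, and a screening tympanogram "to check the function of the middle ear". No eligibility or analysis rule uses these results for the four factors.
- **The only adjustment mentioned (section 2).** The speech-in-noise hypothesis is framed as controlling for hearing deficits. This refers to the degree of hearing loss, not to its causes, and is not carried into 5.5.

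**The concern.** By excluding these factors from the comparators, the protocol treats them as things that would distort a hearing comparison. It then removes them from only one side of each comparison.

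The primary outcome question in 4.2 asks for features of auditory dysfunction that are specific to the disease, and section 2 hypothesises an audiological pattern attributable to iSS. Suppose some siderosis participants have noise, ototoxic, middle-ear or familial hearing loss, and the comparators have been cleared of all four. Part of any observed difference could then belong to those factors. Raw thresholds would be expected to look worse in iSS as a result. Speech-in-noise adjusted for thresholds could move either way. Unless the factors are tabulated, a reader of the results cannot judge how much they contribute.

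**Working it through.** The plan has no power, effect-size or prevalence figure to reproduce; section 7.2.1 says no reliable calculation is possible. The only document inputs are the three eligibility lists, the text of 5.5 and the group size of 20 to 30. Everything else below is assumed and serves only to show scale.

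**1. Shift in the siderosis mean.** Let q be the share of siderosis participants affected and Δ the worsening in each, in SD units. The comparators have q = 0 by design, so the shift is q × Δ.

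- Low: 0.1 × 0.5 = 0.05 SD
- Middle: 0.2 × 1.0 = 0.20 SD
- High: 0.3 × 1.5 = 0.45 SD

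In people, this runs from 2 (10% of 20) to 9 (30% of 30).

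**2. Effect on a nominal 5% test if iSS itself had no effect.** The siderosis variance becomes 1 + q(1−q)Δ². In the middle case this is 1 + 0.2 × 0.8 × 1 = 1.16.

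- 20 per group: SE = √(1.16/20 + 1/20) = 0.329; 0.20/0.329 = 0.61; two-sided rejection rate 9.3%.
- 30 per group: SE = √(1.16/30 + 1/30) = 0.268; 0.20/0.268 = 0.75; rejection rate 11.6%.

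**3. Speech-in-noise after adjusting for thresholds.** With slope b of speech-in-noise on threshold, the adjusted shift is q × (Δ_speech − b × Δ_threshold). Take q = 0.2 and b = 0.5, with positive meaning worse in iSS.

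- The factor worsens both by 1 SD: 0.2 × (1 − 0.5) = +0.10
- It worsens thresholds only: 0.2 × (0 − 0.5) = −0.10
- It worsens speech-in-noise only: 0.2 × (1 − 0) = +0.20

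The planned control for hearing deficits therefore does not remove the problem, and the sign is not fixed.

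**4. Restriction and adjustment use the same information.** Fit a regression with group and one indicator for having any of the four factors; the indicator is zero in every comparator. The group coefficient is the mean of unaffected siderosis participants minus the comparator mean, which is exactly the restricted-set difference. A numerical check gave 0.0666 both ways. So for mean differences the regressions in 5.5 could deliver the correction, if the indicator were named.

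**5. Precision of the restricted comparison.** The 95% half-width is t(0.975, n₁+n₂−2) × √(1/n₁ + 1/n₂), with SD 1 in both sets and 30% of siderosis participants removed.

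| Per group | Full set | Restricted |
|---|---|---|
| 20 | 20 v 20: 0.64 | 14 v 20: 0.71 |
| 30 | 30 v 30: 0.52 | 21 v 30: 0.57 |

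**6. What a change between the two estimates can show.** Dropping participants at random moves the siderosis mean with SD √(1/kept − 1/n). For 20% dropped:

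- 16 of 20 kept: √(1/16 − 1/20) = 0.11
- 24 of 30 kept: √(1/24 − 1/30) = 0.09

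Against a middle-case shift of 0.20, the ratios are 0.20/0.112 = 1.8 and 0.20/0.091 = 2.2. A 95% interval on the change would exclude zero only about 40% to 60% of the time.

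**The case against.** The strongest reply is that the asymmetry is deliberate. iSS is rare, section 7.2.1 wants as many participants as possible, and the comparator exclusions help define what an age-related loss or a normal-hearing control is. This stands as a reason not to change eligibility. It does not supply the missing analysis step.

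A second reply is that the regressions in 5.5, run with a biostatistician, could include the factors. That is correct. A reader might infer that covariate adjustment cannot help because the factors are absent from the comparators. The documents do not support that reading: step 4 shows that adjustment and restriction give the same answer for means. The gap is that neither is stated, and a chi-square test cannot adjust at all.

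A third reply is that the data are largely collected. Full history, otoscopy and air- and bone-conduction audiometry are listed for all groups, and 5.2 adds acoustic reflexes on a middle-ear recorder for the comparators. This also stands. It would go too far to infer that middle-ear status in the comparators goes unexamined. The test list for comparators in 5.2 omits tympanometry while the Appendix 2 schedule marks it for them, and the ARHL and control exclusions differ on dysfunction. These are consistency points, separate from the main one.

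Finally, every size input is assumed and nothing in the documents suggests that the factors are common in iSS. At the low end, 0.05 SD is negligible. This limits the weight of the point but does not remove it.

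**Conclusion.** The point holds as a design asymmetry with no stated analytic answer. Followed as written, the plan could credit to iSS some hearing loss that comes from factors screened out of the comparators only.

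The size is unknown. The range of 0.05 to 0.45 SD in the siderosis mean rests wholly on assumed frequencies (10% to 30%) and effects (0.5 to 1.5 SD). For scale, the difference detectable with 80% power at two-sided 5% is about 0.89 SD with 20 per group and 0.72 SD with 30. The middle-case shift of 0.20 SD is thus well short of producing a convincing difference alone, but enough to inflate one.

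A reader might go further and conclude that the three-group comparison is invalid, or that the siderosis eligibility is wrong. The documents support neither: they give no frequency of these factors in iSS, and broad entry is a reasonable choice in a rare disease. The supported conclusion is that attribution to iSS needs a stated check and a stated limit. This is a worthwhile, inexpensive improvement.

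**What to change.** Leave eligibility unchanged and keep every siderosis participant.

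1. Record the four factors for each siderosis participant from the history and tests already done. Use the broader ARHL wording for the middle ear, which covers dysfunction as well as disease. Tabulate them.
2. Add to 5.5, in words such as these: *The main siderosis-versus-ARHL and siderosis-versus-control hearing comparisons will be repeated in siderosis participants with none of the four comparator exclusion factors. Both estimates will be reported side by side with 95% intervals, as a supportive sensitivity analysis.* For mean differences, adding one any-factor indicator to the regression is equivalent. Section 5.5 should list which comparisons count as main, since 7.2.1 identifies no primary test.
3. Limit the attribution to iSS in the report according to how the two estimates compare, and say that similar estimates do not exclude bias.
4. Separately, reconcile 5.2 with Appendix 2 on tympanometry in the comparators, and 7.1.2 with 7.1.3 on the middle-ear wording.

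**Cost.** A few data fields, one table, and the main hearing comparisons run twice. The restricted intervals are wider (half-width 0.64 to 0.71 SD at 20 per group, 0.52 to 0.57 SD at 30, if 30% are removed and the SD is 1), so the check is imprecise and should not decide any claim.

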### 7.1.3 Control group

Inclusion criteria:

- Adults (male and female) of 18+ years old with no previous diagnosis of hearing loss or no known neurological disorder (including iSS) that affects hearing (control group); we will aim to recruit such participants of 50 years of age and above, however if difficulty with recruitment of such participants arises, we will recruit participants of 18 years of age and above.

Exclusion criteria:

- Individuals with a physical or mental impairment that prevents the potential participant from giving informed consent or undergoing the audiological and assessment
- Individuals younger than 18 years old
- Individuals with a known history of hearing loss (of any cause) or with a known neurological disorder that affects their hearing
- Individuals with history of exposure to high-intensity noise or ototoxic drugs or evidence of middle ear disease or family history of non age-related hearing loss

Participants in the siderosis group will be users of the National Health Service (NHS) and will be recruited from University College London Hospitals (NHS Foundation Trust) London. The ARHL group participants will be recruited from the Adult Audiology Services at University College London Hospitals (NHS Foundation Trust), and will have used the NHS services in the past or will be recruited from the general public. The control group participants will be recruited from the general population. There will be no upper limit to the participants' age.

## 7.2 Sampling

### 7.2.1 Size of sample

Power and sample size calculations cannot be reliably carried out prior to commencing the study as we are restricted by how rare the disease is. Furthermore, there are currently few reports on audiological and vestibular function in iSS in the literature, and where available, these are highly heterogeneous in the testing regimens used. There appears no primary test or indicator that is considered the 'gold standard' test. This heterogeneity means that it is challenging to effectively perform necessary power/sample size calculations. In addition to this, a comprehensive battery of tests will be included in this study, each of which will influence the required sample sizes. Due to its rarity we would like to recruit as many participants with iSS as possible. Reviewing the study for feasibility, however, after 10-15 participants in each arm have been assessed in the study, will allow to establish the variability between the groups and will be used to inform the adjustment to sample size. Furthermore, it will be likely to reflect on the difficulty (or ease) as well as the pace of recruitment of participants into the study.

These preliminary results will be collected and analysed by the research student in collaboration with a designated biostatistician from the UCL and the Biostatistics Office at UCL(H) JRO. A validated statistical software programme will be used to conduct the analysis, which will include all the parameters and assumptions used in the pilot study. Inflation factors and attrition rate will also be accounted for and will be included into sample size calculations.

### **7.2.2 Sampling technique**

Due to rarity of iSS we would like to include as many participants with this diagnosis as possible (to the maximum of 30 participants). The sizes of other two groups will match the siderosis group sample (to the maximum of 30 participants in ARHL and control groups each).

### **7.2.3 Sample identification**

#### Siderosis group:

Potential participants will be identified from the clinical database by a member of the Siderosis/Neurology team at University College London Hospitals (NHS Foundation Trust) which is likely to be one of the largest databases in the UK, due to rarity of the disease and the highly specialist expertise of the Neurology team in this area at University College London Hospitals (NHS Foundation Trust).

#### Age-Related Hearing Loss group:

Potential participants will be identified from the clinical database by a member of the Adult Audiology Services team at University College London Hospitals (NHS Foundation Trust) and will approximate the numbers of the participants in the siderosis group (20-30 participants).

Alternatively, and to maximise the recruitment potential, the age-related hearing loss group

participants may be recruited from the general public (by advertising the study and/or displaying the study posters in community hearing aid centres, AgeUK, the University of Third Age, and through the BRC BioResource Bank at UCLH, dedicated Facebook/social network and online groups.

#### Control group:

Potential participants will be recruited from the general public and will approximate the numbers of the participants in the siderosis group (20-30 participants). In order to best approximate the ages between the groups, we will aim to recruit general public participants of 50 years of age and above, however if difficulty with recruitment of such participants arises, we will recruit participants of 18 years of age and above. The study recruitment posters will be displayed in the public areas such as waiting areas, canteens and cafes in University College London Hospitals (NHS Foundation Trust) or by advertising the study and/or displaying study posters in community hearing aid centres, AgeUK, the University of Third Age, and through the BRC BioResource Bank at UCLH and dedicated Facebook/social network and online groups.

### **7.3 Recruitment**

Three cohorts (of approximately 20-30 participants in each) will be recruited into the study, comprising of:

1. Cohort of participants with the diagnosis of iSS (siderosis group). These will be recruited from University College London Hospitals (NHS Foundation Trust).
2. Cohort of participants with the diagnosis of ARHL (ARHL group). These will be recruited from the Adult Audiology Centre, University College London Hospitals (NHS Foundation Trust) or from the general public (by advertising the study and/or displaying the study posters in community hearing aid centres, AgeUK, the University of Third Age, and through the BRC BioResource Bank at UCLH and dedicated Facebook/social network and online groups).
3. Cohort of individuals with no previous history of hearing problems (control group). These will be recruited from the general population. The study recruitment posters will be displayed in the public areas such as waiting areas, canteens and cafes in University College London Hospitals (NHS Foundation Trust) or by advertising the study and/or displaying study posters in community hearing aid centres, AgeUK, the University of Third Age, and through the BRC BioResource Bank at UCLH and dedicated Facebook/social network and online groups.

Participant's journey from the point of identification to the recruitment into the study (siderosis group):

Patients with the diagnosis of iSS who attend Neurology Clinics at University College London Hospitals (NHS Foundation Trust) will be identified from a prospectively collected patient database of all known referrals with iSS. A member of the clinical team will approach the potential participant in the clinical setting to let them know that the study is taking place and asking their permission to be contacted by the research student. Alternatively, a member of the clinical team will contact the potential participant informing them of the study taking place and asking their permission to be contacted by the research student. If consent is given to be contacted, the research student will send a participant information sheet together with a study invitation letter and a pre-stamped self-addressed envelope to the identified potential participants.

There will be no time-limit to the participants' decision to take part in the study.

If willing to participate, the patients will be contacted by the research student to provide the participant information sheet and the study invitation letter. The study participation schedule will be discussed between the potential participant and the research student and the clinic appointment time (as scheduled by the clinical team) will be confirmed. The first/initial visit will take place during the clinical visit to Neuro-otology services at the University College London Hospitals (NHS Foundation Trust). The research student will ask the potential participant if willing to complete self-report questionnaires at home prior to their visit, and if so, these will be sent out to the potential participant to fill in at home ahead of their visit (as a time-saving measure). These will not be collected only after the written consent has been obtained by the participant to take part in the study.

During the first/initial study visit to University College London Hospitals (NHS Foundation Trust), the participant's questions pertaining to the study will be answered by the research student. The candidate's eligibility to participate in the study will be determined at this point, and the formal written consent to participate in the study will be obtained. The questionnaires that have been distributed to the participants will be collected only after obtaining the formal written consent to take part in the study. No study related procedures will be performed without the participant's consent. The participant's decision to take part in the study will be documented in the medical notes. A copy of the formal written consent will be given to the participant.

Where the participant is ineligible, this, together with the reasons for ineligibility, will be documented by the clinical team member in the participant's medical notes.

Participant's journey from the point of identification to the recruitment into the study (ARHL group):

Patients with the diagnosis of ARHL who previously attended Adult Audiology Centre University College London Hospitals (NHS Foundation Trust) will be identified from the patient database. A member of the clinical team will approach the potential participant in the clinical setting to let them know that the study is taking place and asking their permission to be contacted by the research student. Alternatively, a member of the clinical team will contact the potential participant informing them of the study taking place and asking their permission to be contacted by the research student. If consent is given to be contacted, the research student will send a participant information sheet together with a study invitation letter and a pre-stamped self-addressed envelope to the identified potential participants.

Alternatively, and to maximise the recruitment potential, the age-related hearing loss group participants may be recruited from the general public by advertising the study and/or displaying the study posters in community hearing aid centres, AgeUK, the University of Third Age, and through the BRC BioResource Bank at UCLH and dedicated Facebook/social network and online groups. The advertisement/study poster will contain the contact details of the research student. Potential participants interested in the study will be able to contact the research student and will be provided with a participant information sheet together with an invitation letter upon contact. There will be no time limit to the participants' decision to take part in the study. If willing to participate, the potential participant will contact the research student and will be invited to attend University College London Hospitals (NHS Foundation Trust) or the UCL Ear Institute. The research student and the potential participant will agree on a suitable appointment day and time. The research student will ask the potential participant if willing to complete self-report questionnaires and if so, these will be sent out to the potential participant to complete at home (as a time-saving measure). These will not be collected until the appointment and only after the written consent has been obtained by the participant to take part in the study.

During the visit to University College London Hospitals (NHS Foundation Trust) or the UCL Ear Institute, the participant's questions pertaining to the study will be answered by the research student. The candidate's eligibility to participate in the study will be determined at this point, and the formal written consent to participate in the study will be obtained. The questionnaires that have been sent out to the participant will be collected at this stage and only after obtaining the formal written consent from the participant to take part in the study. No study related procedures will be performed without the participant's consent. The participant's decision to take part in the study will be documented in the medical notes (where applicable). A copy of the formal written consent will be given to the participant.

Where the participant is ineligible, this, together with the reasons for ineligibility, will be documented by the clinical team member in the participant's medical notes (where applicable) or in the study file.

[figure not shown]
Participant's journey from the point of identification to the recruitment into the study (control group):

The control group participants will be recruited from the general public. The study recruitment posters will be displayed in the public areas such as waiting areas, canteens and cafes in University College London Hospitals (NHS Foundation Trust) or by advertising the study and/or displaying study posters in community hearing aid centres, AgeUK, the University of Third Age, and through the BRC BioResource Bank at UCLH and dedicated Facebook/social network and online groups.

The advertisement/study poster will contain contact details of the research student. Potential participants interested in the study will be able to contact the research student and will be provided with a participant information sheet together with an invitation letter upon contact. There will be no time limit to the participants' decision to take part in the study. If willing to participate, the potential participant will contact the research student and will be invited to attend University College London Hospitals (NHS Foundation Trust) or the UCL Ear Institute. The research student and the potential participant will agree on a suitable appointment day and time. The research student will ask the potential participant if willing to complete self-report questionnaires and if so, these will be sent out to the potential participant to complete at home (as a time-saving measure). These will not be collected until the appointment and only after the written consent has been obtained by the participant to take part in the study.

During the visit to University College London Hospitals (NHS Foundation Trust) or the UCL Ear Institute, the participant's questions pertaining to the study will be answered by the research student. The candidate's eligibility to participate in the study will be determined at this point, and the formal written consent to participate in the study will be obtained. The questionnaires that have been sent out to the participant will be collected at this stage and only after obtaining the formal written consent from the participant to take part in the study. No study related procedures will be performed without the participant's consent. The participant's decision to take part in the study will be documented in the study file. A copy of the formal written consent will be given to the participant.

Where the participant is ineligible, this, together with the reasons for ineligibility, will be noted and documented in the study file.

